### 14 1. Background

15 Type 2 diabetes is prevalent and poses a great burden in the world. Data from the International Diabetes Federation (IDF) showed that the number of diabetic patients had reached 451 million in 16 17 2017, and it will rise to 693 million by 2045. While management of hyperglycemia in well-targeted 18 range can markedly improve diabetic complications and reduce mortality in diabetic patients. 19 Many type 2 diabetic patients require insulin therapy for glycemic control in the course of disease 20 progression. However, two-thirds of insulin users sustain glycated hemoglobin (HbA1c) levels 21 above 7.0% (53 mmol/L) and more than a third sustain HbA1c levels higher than 9.0% (75 22 mmol/L) mainly due to inaccurate and inertia titration of insulin dosage.

23 Effective and safe insulin therapy is essential for glycemia management in type 2 diabetic 24 patients. The glycemic targets achieved respond to acute illness, changes in the amounts and timing 25 of dietary intake, physical exercise and anti-diabetic medication etc.. Moreover, conventional insulin therapy increases the risk of hypoglycemia, which is also associated with increased 26 27 morbidities and length of hospital stay. Therefore, personalized and frequent dosage titrations are 28 indispensable to overcome constant variations in insulin requirements. The glycemia management 29 in type 2 diabetes patients has long been hindered by the need for experienced physicians to make 30 insulin dosage titration. Consequently, glycemic control is often inadequate. To achieve this goal, 31 an accurate and real-time insulin dosage titration system is needed at an individual level. Of note, 32 current tools are mostly created based on general guidelines and cannot meet the need for clinicians 33 to precisely titrate insulin dosage.

Artificial intelligence (AI) approaches have emerged as potentially powerful tools to mine electronic health records (EHRs) data to aid in disease diagnosis and management , mimicking and perhaps even augmenting the physicians in clinical decision-making. The application of artificial intelligence has been involved in image recognition of diabetic retinopathy and risk prediction for diabetes. The recent promising work on EHRs-derived modelling suggests that the incorporation of machine learning may enable clinical decisions of insulin dosage titration.

40 In the previous study, we have built and validated an artificial intelligence-based insulin 41 clinical decision support system (iNCDSS) based on the data retrospectively obtained from the EHRs of hospitalized type 2 diabetic patients who received insulin therapy from January 2013 to 42 43 October 2018 in the Department of Endocrinology and Metabolism, ZhongShan Hospital, 44 Shanghai, China. After the EHR notes were annotated using a deep NLP information extraction 45 model, we used a machine-learning method, eXtreme Gradient Boosting (XGBoost) to derive an 46 algorithm that provides insulin dosage recommendations. The model performed well with a mean 47 absolute relative difference (MARD)<10%. In the present study, we conduct a multicenter, 48 randomized controlled trial to evaluate the efficacy and safety of iNCDSS system on glycemic 49 control in type 2 diabetic patients who received insulin therapy in the clinical setting.

#### 50 2. Study Objectives

The objective of the study is to evaluate the efficacy and safety of insulin dosage titration by the iNCDSS system as compared with senior physicians in glucose control in type 2 diabetic patients treated with subcutaneous insulin injection. We hypothesize that the glycemic control in type 2 diabetic patients receiving insulin dosage titrated according to the iNCDSS system recommendation is non-inferior to that in patients receiving insulin dosage titrated by senior physicians assessed by the percentage of time of sensor glucose concentration in the targeted range.

57 **2.1 Primary Objectives** 

58 To evaluate the effect of insulin dosage titration according to iNCDSS system on glucose control

- assessed by percentage of time of sensor glucose measurement in target range (TIR) of 3.9-10.0
- 60 mmol/L during the 5 days trial period as compared to senior physicians in type 2 diabetic patients

61 with insulin therapy.

## 62 2.2 Secondary Objectives

- (1) To evaluate the effect of insulin dosage titration according to iNCDSS system on glucose
  control assessed by the percentage of time of sensor glucose concentration above range
  (10.1-13.9 mmol/L or >13.9 mmol/L) or below range (3.0-3.8 mmol/L or <3.0 mmol/L) during

  the 5 days trial period as compared to senior physicians in type 2 diabetic patients with insulin
  therapy.
- (2) To evaluate the effect of insulin dosage titration according to iNCDSS system on mean sensor
  glucose concentration, glucose management indicator (GMI), and glycemic variability (%CV)
  during the 5 days trial period as compared to senior physicians in type 2 diabetic patients with
  insulin therapy.
- 72 (3) To evaluate the effect of insulin dosage titration according to iNCDSS system on mean
   73 pre-meal and pre-bed capillary glucose concentration at each defined time during the 5 days
   74 trial period as compared to senior physicians in type 2 diabetic patients with insulin therapy.
- 75 (4) To evaluate the risk of hypoglycemia of insulin dosage titration according to iNCDSS system
   76 as compared to senior physicians in type 2 diabetic patients with insulin therapy.
- To compare the mean total daily insulin dose in type 2 diabetic patients receiving insulin
   titration by iNCDSS system and by senior physicians.

## 79 3. Study Design

### 80 3.1 Design Overview

81 The study is a multicenter, patient-blind, and randomized controlled trial to evaluate the efficacy 82 and safety of iNCDSS in the clinical application. Eligible patients are randomly allocated into two 83 groups at a ratio of 1:1 after screening and run-in period. Randomization is stratified according to 84 sites and baseline HbA1c level. Patients in the intervention group receive insulin dosage titration set 85 by the iNCDSS assisted system and patients in the control group receive insulin dosage titration set 86 by senior physicians. A total of 142 type 2 diabetic patients will be enrolled and this study will be 87 conducted in the wards of Department of Endocrinology and Metabolism in Zhongshan Hospital, 88 Xuhui Central Hospital, and Shanghai Fifth People's Hospital, Fudan University. All patients are 89 studied for 5 consecutive days. Continuous glucose monitoring (CGM) is performed using flash 90 glucose monitoring (Abbott Freestyle Libre, USA) to measure the primary outcome of the 91 percentage of time of sensor glucose concentration in the target range during the 5 days trial period. 92 The CGM data will be analyzed retrospectively, and the treatment will not be influenced by data 93 gained by CGM. 94 **3.2 Study Population** 

- Eligible patients should meet the inclusion criteria and be excluded from the study if they meet anyof the exclusion criteria.
- 97 **3.2.1 Inclusion criteria**
- 98 Patients included in this study should meet the following criteria:
- 99 1) Patients with type 2 diabetes;
- 100 2) Aged  $\geq 18$  years old;
- 101 3) Treated with diet alone, any combination of oral antidiabetic agents, and/or insulin

therapy for at least 3 months;

103 4) HbA1c: 7.0%-11.0%.

104 **3.2.2 Exclusion criteria** 

- 105 Patients will be excluded from this study if they meet any of the following exclusion criteria:
- Acute diabetic complications including diabetic ketoacidosis or hyperglycemic
   hyperosmolar state;
- 108 2) BMI≥45 kg/m^2;
- 109 3) Women who are pregnant or breast-feeding;
- 110 4) Subjects with severe cardiac, hepatic, or renal diseases;
- 111 5) Subjects with any psychiatric or psychological diseases;
- 112 6) Subjects with severe oedema, infections, or peripheral circulation disorders;
- 113 7) Patients plan to receive surgery during hospitalization;
- 114 8) Subjects who cannot comply with the protocol.

## 115 **3.3 Randomization and masking**

## 116 **3.3.1 Randomization**

Randomization will be conducted by the statistician of Department of Statistics, Public Health and Preventive Medicine, Fudan University, and generated by SAS software. The randomization scheme is generated and concealed until an eligible participant is ready to be randomized. Prior to randomization, the study coordinator should confirm that all screening procedures have been completed, the participant meets all eligibility criteria, and all required baseline data have been collected. Randomization is stratified according to sites and HbA1c levels (<8.0% or  $\geq$ 8.0%) and

eligible patients are randomly allocated into intervention and control groups at a ratio of 1:1.

## 124 3.3.2 Masking

Treatment allocation will be masked from participants and be concealed with sealed opaque envelopes. Although this is a single-blinded trial, the research assistants who collect study outcome data will be masked to participants' intervention assignment. In addition, the adjudicators for end-points will not be aware of study-group assignments.

## 129 **3.4 Study Procedure**

- 130 The study consists of the following periods: 1) a screening period before admission (<2 weeks); 2) a
- run-in period on the first day of hospitalization; and 3) a 5-days intervention period duringhospitalization (Figure 1).
  - **Screening Period Run-in Period** Intervention Period ----- <2 weeks 1 day 5 days ----iNCDSS treatment (intervention group) Reassess for eligibility Obtain informed Physician reassess the patient to continue consent and screen and start initial cycle of for eligibility insulin regimen treating or discharge Senior physician treatment (control group) Figure 1. Flow chart

### 135 **3.4.1 Screening period**

133 134

136 T2D patients will be eligible to be screened in the study. The information about the study will be

137 provided to patients in oral and in writing. Written informed consent for participation in the study is

obtained before performing any study-specific screening tests or evaluations. After signing the informed consent form, patients will be assigned a screening number and assessed for eligibility.

- 140 Clinical characteristics and blood HbA1c level are evaluated during the screening period. The
- screening period will be completed until admission.

## 142 **3.4.2 Run-in period**

- 143 The first day of hospitalization is the run-in period. Patients are reassessed for eligibility with regard
- to HbA1c results. Height, body weight, HbA1c level, and previous diabetes treatments are recorded. In the run-in period, the initial insulin regimen and dose are determined by the physician based on guidelines and patient's disease status. The iNCDSS system fetches the patient's clinical information and initial insulin regimen and dosage and then recommends the next insulin dose. All obligatory assessments should be completed in this period. The data obtained from clinical
- evaluation and laboratory tests for screening are used for baseline assessment as well. After the
- run-in period, subjects will be randomly assigned to the intervention group and the control group at
- 151 1:1 ratio.

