# 152 **3.4.3 Intervention period**

## 153 **3.4.3.1 Intervention group**

154 The iNCDSS system is an artificial intelligence-based insulin clinical decision support system using 155 an artificial intelligence-based system to extract clinically relevant features from EHR notes to 156 mimic the insulin dosage titration by senior endocrinology physicians. The iNCDSS is installed in 157 the doctor's advice interface of the health information system (HIS) to real-time read patient 158 information and provide insulin dosage regimens. In the intervention group, insulin dosage is modified and titrated according to the iNCDSS recommendation. The physicians can review the 159 160 current recommendation and choose "accept" or "reject". The nurse staff will conduct insulin 161 injection according to the doctor prescribed. To assess compliance, physicians' adherence to the 162 recommended insulin dosage will be documented and any deviation from recommended dosage to 163 administered insulin dosage will be recorded.

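### iNCDSS recommends a dose before randomisation, and nothing in the protocol keeps it from the physicians who may later titrate control patients

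*Protocol*

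**What the plan says.** Protocol section 3.4.2 (Run-in period) describes the first hospital day, which every patient passes through. It opens with an eligibility check: "Patients are reassessed for eligibility with regard" to HbA1c. A physician then sets the starting regimen. iNCDSS next takes in the clinical data together with the "initial insulin regimen and dosage and then recommends the next insulin dose". Only at the end does allocation follow: after the "run-in period, subjects will be randomly assigned to the intervention group and the control group at" a 1:1 ratio.

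Section 3.4.3.1 (Intervention group) says where the system sits: in the doctor's "advice interface of the health information system (HIS) to real-time read patient" information and supply dosing. That sentence describes the system in general. The next step, in which "The physicians can review the" current recommendation and accept or reject it, belongs to the intervention group. Adherence to the recommendation is also documented under that heading.

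Section 3.4.3.2 gives control titration to senior physicians and names SMBG and clinical information as its basis. iNCDSS output is not among the sources. Section 3.3.2 masks participants, outcome data collectors and endpoint adjudicators. Treating physicians are not listed.

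**The concern.** The comparator is the senior physician's own titration. If a physician has already seen what iNCDSS would give a patient who is then allocated to control, the first titration decision in that patient may carry information from the test system.

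In a superiority trial such leakage costs power. Here it works the other way: it shrinks any true deficit of iNCDSS towards zero, so a system that is worse by the full margin is more likely to be declared non-inferior. Analysis by intention to treat does not correct this. The protocol also describes no comparison of control orders with the recommendation, so the leakage would probably go unnoticed.

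The protocol sets such a barrier elsewhere. Section 3.1 says that CGM data are analysed retrospectively and are not to influence treatment. No matching statement covers iNCDSS output in control patients. A statistical analysis plan could not supply one, because what appears on the ordering screen is a matter of trial conduct.

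**Working it through.** **Sequence in the text**

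1. Section 3.4.2: the recommendation is generated in the run-in, without restriction by arm. None is possible, because allocation comes later.
2. Section 3.3.1: allocation is 1:1, so about half of the patients with a run-in recommendation become controls.
3. Section 3.4.3.1: the system is installed in the ordering interface that physicians use.
4. Section 3.3.2: treating physicians are not masked. No section hides the output in the run-in or from physicians treating controls.

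Steps 1 to 4 establish that viewing is not prevented. They do not establish that it happens.

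**Inputs for an illustration of size**

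Section 6.1 gives SD 12 percentage points, margin 6 points, one-sided alpha 0.025, power 80%, dropout about 10% and a total of 142.

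**The plan's own figure**

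n per arm = 2 × (1.960 + 0.842)² × 12² / 6² = 62.8, so 63 per arm and 126 in total; 126 / 0.9 = 140. The t-based calculation gives 64 per arm; 64 × 1.1 = 70.4, rounded up to 71 per arm, or 142. The stated sample size reproduces and is not affected by this point.

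**Effect of shrinkage on the error rate**

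Take 64 evaluable patients per arm and a true difference exactly at the margin, -6 points.

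SE = 12 × √(2/64) = 2.12 points.

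Let c be the fraction of the difference lost because control dosing is influenced. The expected difference becomes -6 × (1 - c), and

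P(declare non-inferiority) = 1 - Φ(1.960 - 6c / 2.12).

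| c (assumed) | Expected difference | 6c / SE | P(declare non-inferiority) |
|---|---|---|---|
| 0% | -6.0 | 0 | 2.5% |
| 5% | -5.7 | 0.14 | 3.4% |
| 10% | -5.4 | 0.28 | 4.7% |
| 20% | -4.8 | 0.57 | 8.2% |

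The protocol gives no value for c. The 20% end is one day out of five (1/5). It requires that the run-in recommendation fully determines day 1 in every control patient, that each day contributes equally to the difference, and that the influence ends with day 1.

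**The case against.** The best reply is that exposure is inferred. Section 3.4.2 does not say to whom the recommendation goes or that it is displayed. It can be read as background preparation, so that a dose is ready once a patient is allocated to iNCDSS. Review with accept or reject is described only for the intervention group. This stands in part: the text does not show that physicians see the output for future controls. It does not remove the point, because describing how one arm uses the screen does not close it for the other.

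A second reply concerns size. The text speaks of one next dose, not a day of doses. In the scenario used, senior physicians would also have to follow an inferior recommendation rather than their own judgement. This stands. The upper end is extreme, and at c = 0 there is no effect.

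A reader might go further and infer that entry to the trial is selected on the recommendation, since eligibility is reassessed on the same day. The protocol does not support that:

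- Section 3.4.2 lists the HbA1c check first, and no eligibility criterion refers to iNCDSS output.
- Section 3.3.1 requires that prior to "randomization, the study coordinator should confirm that all screening procedures have been completed, the participant meets all eligibility criteria", and the "scheme is generated and concealed until an eligible participant is ready to be randomized". Seeing a dose would not reveal the arm.
- Any such selection would precede allocation and affect both arms alike. It would bear on who is studied, not on the comparison.

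**Conclusion.** The concern holds as a gap in the stated sequence. A recommendation from the test system exists before randomisation for patients who will become controls, it comes from a system installed in the ordering interface, and nothing withholds it from unmasked physicians. Any influence on control dosing would favour non-inferiority.

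The size is unknown. Under the assumed range of 0 to 20% shrinkage, with 64 per arm, SD 12 and a true difference at the margin, the false non-inferiority rate lies between 2.5% and about 8%. If iNCDSS and physicians are truly equivalent, shrinkage changes nothing. The figures illustrate direction and order of magnitude and do not estimate bias in this trial. The documents do not support a claim that contamination occurs.

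**What to change.** Add to section 3.4.2 that iNCDSS may load patient data during the run-in, but that no recommendation is displayed until after randomisation, and then only for patients allocated to iNCDSS. State in section 3.4.3.2 that the output stays hidden for control patients throughout the 5 days. If the system already works this way, saying so settles the point.

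The cost is a few sentences and a display restriction in the hospital information system. Its feasibility is assumed, because the protocol does not describe how the system's permissions work. Sample size, visits and analysis are unchanged.

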# 152 **3.4.3 Intervention period**

## 153 **3.4.3.1 Intervention group**

154 The iNCDSS system is an artificial intelligence-based insulin clinical decision support system using 155 an artificial intelligence-based system to extract clinically relevant features from EHR notes to 156 mimic the insulin dosage titration by senior endocrinology physicians. The iNCDSS is installed in 157 the doctor's advice interface of the health information system (HIS) to real-time read patient 158 information and provide insulin dosage regimens. In the intervention group, insulin dosage is modified and titrated according to the iNCDSS recommendation. The physicians can review the 159 160 current recommendation and choose "accept" or "reject". The nurse staff will conduct insulin 161 injection according to the doctor prescribed. To assess compliance, physicians' adherence to the 162 recommended insulin dosage will be documented and any deviation from recommended dosage to 163 administered insulin dosage will be recorded.

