### 164 **3.4.3.2** Control group

- Patients in the control group receive insulin dosage titration set by senior physicians based onSMBG and clinical information.
- 167 **3.5 Study Outcomes**
- 168 **3.5.1 Primary outcomes**
- 169 The percentage of time of sensor glucose measurements in targeted range (3.9-10 mmol/L) during
- 170 the 5-days trial period.
- 171 **3.5.2 Secondary outcomes**
- 1. The percentage of time of sensor glucose measurement above range (10.1-13.9 mmol/L) during
  the 5 days trial period;
- 174
  2. The percentage of time of sensor glucose measurement above range (>13.9 mmol/L) during the
  175
  5 days trial period;
- 176 3. The percentage of time of sensor glucose measurement below range (3.0-3.8 mmol/L) during
  177 the 5 days trial period;
- 4. The percentage of time of sensor glucose measurement below range (<3.0 mmol/L) during the

  5 days trial period;
- 180 5. The mean sensor glucose concentration;

- 181 6. The glucose management indicator (GMI);
- 182 7. The glycemic variability (%CV);
- 183 8. The mean pre-meal and pre-bed capillary glucose concentration at each defined time based on
- 184 SMBG;
- 185 9. The risk of incidence of hypoglycemia events;
- 186 10. The risk of incidence of hyperglycemic events;
- 187 11. The mean total daily insulin dose.

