### 265 6.2 Data Analysis and Interpretation

Values are presented as mean (SD), median (IQR) or number (%), unless stated otherwise. All analyses are performed by intention-to-treat, and all patients who have available CGM data are 268 included in the primary analysis and all secondary analyses unless otherwise noted. All efficacy 269 outcomes and continuous glucose monitoring based outcomes are summarized and analyzed using 270 the intervention period and intention-to-treat analysis set, and safety analyses included all data up to 271 the end of the study. The primary and secondary outcomes are compared between the two groups 272 with a linear mixed-effect regression model. Missing data are not imputed. The noninferiority 273 hypothesis is tested for the primary outcome by estimating the difference in the percentage of sensor 274 glucose measurement in TIR between the iNCDSS group and the physician group, and the lower limit of 95% CI of -6.0% is estimated as the noninferiority threshold. The proportion of participants 275 276 with events (capillary glucose concentrations <3.0 mmol/L, <2.2 mmol/L, >20.0mmol/L, and/or 277 ketoacidosis) in each group is compared with Fisher's exact test. Compliance is calculated as the 278 percentage of the number of insulin orders where dosages are actually ordered according to 279 iNCDSS recommendation against the total number of insulin orders. All statistical analyses are 280 performed with the use of SAS 9.3 software and R software.

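### The hypothesis concerns dosing according to the iNCDSS recommendation, but the intention-to-treat analysis tests iNCDSS with physician review and override, and no adherence-based analysis supports a claim about the algorithm itself

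*Protocol*

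**What the plan says.** - **Hypothesis (Section 2).** Non-inferiority in time in range (TIR) is hypothesised for patients receiving "insulin dosage titrated according to the iNCDSS system recommendation", compared with titration by senior physicians.
- **Intervention arm (Section 3.4.3.1).** Physicians look at the "current recommendation and choose 'accept' or 'reject". Nurses then give the "injection according to the doctor prescribed". Adherence to the "recommended insulin dosage will be documented and any deviation from recommended dosage to" the dose administered is recorded.
- **Control arm (Section 3.4.3.2).** "Patients in the control group receive insulin dosage titration set by senior physicians", on the basis of SMBG and clinical information.
- **Analysis (Section 6.2).** "All analyses are performed by intention-to-treat, and all patients who have available CGM data are" included in the primary and secondary analyses. Non-inferiority is judged by the lower 95% confidence limit against -6.0%. Compliance is the "percentage of the number of insulin orders where dosages are actually ordered according to" the iNCDSS recommendation, out of all insulin orders. It is not linked to any efficacy analysis.

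**The concern.** The hypothesis and the analysis have different targets. Section 2 is about doses that follow the algorithm. The analysis compares the arms as randomised, and in the intervention arm some doses may be ones that a physician chose after rejecting the algorithm's.

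In a superiority trial this mixing would make a positive result harder to reach. In a non-inferiority trial, any replacement of algorithm doses by comparator-like doses pulls the difference towards zero, which favours the claim. A positive result could then mean that the algorithm doses as well as senior physicians, or that it doses worse and physicians corrected it. The order-level data that could help separate the two are collected, but they enter only a summary percentage.

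**Working it through.** **Inputs from the protocol.** Section 6.1 gives SD 0.12 (12 points of TIR), margin 6 points, one-sided alpha 0.025, power 80%, dropout about 10% and total 142. Section 3.3.1 gives 1:1 allocation.

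**Inputs assumed.** The override rate is not stated, so compliance c (the share of orders given as recommended) is varied. Two further assumptions are that a rejected order performs like a control order, and that the effect dilutes linearly: expected intention-to-treat difference = c × full-adherence difference.

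**Step 1: the stated sample size.** With a true difference of zero, the normal approximation gives n per arm = 2 × (1.96 + 0.84)² × (12/6)² ≈ 63. The t-based calculation needs 64 per arm (power 80.2%). Then 128/0.9 = 142.2, which matches the stated 142. The steps below use 64 evaluable patients per arm.

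**Step 2: standard error.** SE = 12 × √(2/64) = 2.12 points.

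**Step 3: chance of declaring non-inferiority when the algorithm is inferior under full adherence.** For a full-adherence deficit d, P = Φ((6 − c·d)/2.12 − 1.96).

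| Compliance c | d = 6: diluted deficit | P | d = 8: diluted deficit | P |
|---|---|---|---|---|
| 100% | 6.0 | 2.5% | 8.0 | 0.2% |
| 90% | 5.4 | 4.7% | 7.2 | 0.6% |
| 80% | 4.8 | 8.2% | 6.4 | 1.6% |
| 70% | 4.2 | 13.3% | 5.6 | 3.8% |
| 60% | 3.6 | 20.4% | 4.8 | 8.2% |

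The noncentral t (126 df) gives 4.7%, 8.1%, 13.2% and 20.1% for d = 6 at 90%, 80%, 70% and 60%, so the approximation is adequate. An 8-point deficit at 75% compliance appears as 0.75 × 8 = 6 points, exactly at the margin.

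**Step 4: cost of adjusting for compliance.** Under the same model, and treating c as fixed, the full-adherence estimate is the intention-to-treat difference divided by c, with standard error 2.12/c. At c = 0.80 the standard error is 2.65. Power at a true difference of zero is Φ(6/2.65 − 1.96) ≈ 62%. The same approximation without adjustment gives Φ(6/2.12 − 1.96) ≈ 81%.

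**The case against.** The strongest defence is that override is part of the intervention. The Background and Section 3.4.3.1 call iNCDSS a clinical decision support system, Section 3.1 speaks of an iNCDSS assisted system, and the accept-or-reject step sits inside the description of the intervention arm. On that reading a rejection is the randomised strategy working as designed, and intention-to-treat tests that strategy at its nominal 2.5%. This stands. It is why intention-to-treat should remain primary. It does not remove the mismatch with Section 2, which words the hypothesis as dosing according to the recommendation.

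Three further objections also carry weight:

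- **Replacement by control treatment is an inference.** A reader might infer that every rejected recommendation becomes a control dose. The protocol says only that nurses give what the doctor prescribed. It does not state what follows a rejection, or that the rejecting doctor is a senior physician like those in the control arm. If overriding doctors dosed worse than control, the dilution would shrink or could reverse. If they rejected mainly the worst recommendations, linear dilution would understate it.
- **Supportive analysis sets are often left to an SAP, which is not shown.** Their absence from the protocol would not by itself be a fault. The point rests on what Section 6.2 does fix, namely that all analyses are intention-to-treat.
- **Adherence-based sets have their own bias.** Keeping only patients whose recommendations were mostly accepted selects on physician decisions made after randomisation. If rejections cluster in difficult patients, that set could favour iNCDSS. Such an analysis can therefore support the primary result but should not gate it.

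**Conclusion.** The point holds as a mismatch between the hypothesis and what is tested. As planned, the trial can support a conclusion about iNCDSS with physician review and override. It cannot, on intention-to-treat alone, support one about the algorithm's own dosing.

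For that second claim, and a full-adherence deficit equal to the 6-point margin, the illustrative false non-inferiority rate is about 5% at 90% compliance, 8% at 80% and 13% at 70%, against 2.5%. This depends on an override rate that the protocol does not give, on control-like results after rejection, and on linear dilution. If compliance is close to complete, the difference between the two claims is small.

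Two stronger readings are not supported. The documents do not show that the primary test has an inflated error rate, since for the override-permitted strategy it does not. Nor do they show that intention-to-treat is the wrong primary analysis.

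**What to change.** 1. In Section 2 and in the planned conclusion, name the tested strategy as iNCDSS with physician review and override.
2. In Section 6.2, replace the statement that all analyses are intention-to-treat. Make intention-to-treat primary and add a pre-specified supportive adherence-based analysis: a per-protocol analysis, a randomisation-based compliance-adjusted estimate, or both. Base it on the order-level deviations already recorded in the intervention arm, and report it against the same -6-point margin.
3. State that any claim about the algorithm's own dosing will be made only if the supportive analysis is consistent with the primary result, and define beforehand what counts as consistent. Do not make it a condition for the primary conclusion on the override-permitted strategy.

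The cost is protocol wording and one or two extra analyses; the sample size does not change. The supportive analyses will be less precise (power about 62% for the compliance-adjusted estimate at 80% compliance), and the per-protocol set is not protected by randomisation. A per-protocol criterion for the control arm may need data that the protocol does not say are recorded, because adherence is documented only for the intervention arm. No change to the accept-or-reject step or to any dosing rule is implied.
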